13.5. Vital Signs

Vital signs, BSA and weight will be measured at the time points specified in the [APPENDIX 1](#). Vital signs (including systolic and diastolic BP, heart rate, respiratory rate and body temperature) will be measured by the investigator or the designee. Body temperature recorded in Fahrenheit (°F) will be converted to Celsius (°C). Height will be collected once in Screening Period and will be listed with demographics in [Section 7.1](#). BSA will be calculated based on Mosteller method (Mosteller et al 1987) with two decimal places in each cycle:

$$\text{BSA(m}^2\text{)} = ([\text{Height(cm)} \times \text{Weight(kg)}]/3600)^{1/2} \text{ or } ([\text{Height(in)} \times \text{Weight(lb)}]/3131)^{1/2}$$

Descriptive statistics for actual values and changes from baseline of vital signs, weight and BSA will be presented by treatment group and visit for the Safety population. All vital signs, weight and BSA data will be listed by treatment group and visit.

13.6. Electrocardiogram

A 12-lead ECG will be performed at the time points specified in the [APPENDIX 1](#). All scheduled 12-lead ECGs must be performed after the patient has rested quietly for at least 5 minutes in the supine position.

Findings will be classified as {‘Normal’, ‘Abnormal, not clinically significant’ and ‘Abnormal, clinically significant’}. The number and percentage of patients will be provided, by treatment group and visit for the Safety population, in the form of a shift table to detect changes from baseline. All ECG data will be listed by treatment group and visit.

13.7. Hypersensitivity Monitoring

Hypersensitivity will be assessed by vital sign monitoring (including systolic and diastolic BP, heart rate, respiratory rate and body temperature) within 15 minutes before the study drug infusion, within 15 minutes after the end of the study drug infusion and at 60 minutes (\pm 15 minutes) after the end of the study drug infusion on each dosing day.

The number and percentage of patients with a clinically notable vital sign hypersensitivity result will be presented by treatment group, visit, time point and parameter for the Safety population.

The criteria for clinically notable results are defined as follows:

Parameter	Low	High
Systolic blood pressure (mmHg)	≤ 90	≥ 160
Diastolic blood pressure (mmHg)	≤ 50	≥ 90
Heart rate (beats per minute)	≤ 50	≥ 100
Respiratory rate (breaths per minute)	≤ 12	≥ 20
Body temperature (°C)	≤ 35.0	≥ 38.0

In addition, hypersensitivity should be monitored by routine continuous clinical monitoring including ECG (3-lead or 12-lead) monitoring at 60 minutes (\pm 15 minutes) after the end of the study drug infusion. Findings will be classified as {‘Normal’, ‘Abnormal, not clinically significant’ and ‘Abnormal, clinically significant’}. The number and percentage of patients will be provided by treatment group and visit for the Safety population in the form of a shift table to detect changes from baseline. All hypersensitivity data will be listed by treatment group, visit and time point.

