5.5. Definition of Baseline

The baseline value will be considered to be the last non-missing value before the first administration of study drug. Post-baseline values will be considered to be all values collected after the first administration of study drug.

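### SAP 13.7 labels any vital sign outside a fixed limit a hypersensitivity result, even before the infusion, and plans no same-day pre-to-post summary

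*SAP*

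**What the plan says.** SAP section 13.7 takes five vital signs on each dosing day at three times: "within 15 minutes before the study drug infusion, within 15 minutes after the end of the study drug infusion", and 60 minutes (±15) after the end. The planned summary is the number and percentage of "patients with a clinically notable vital sign hypersensitivity result will be presented by treatment group, visit, time point and parameter", in the Safety population.

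"The criteria for clinically notable results are defined as follows" introduces a table of absolute limits: systolic pressure ≤90 or ≥160 mmHg, diastolic ≤50 or ≥90 mmHg, heart rate ≤50 or ≥100 per minute, respiratory rate ≤12 or ≥20 per minute, temperature ≤35.0 or ≥38.0 °C. No time point is exempt, and no element of change is included.

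The ECG part of the same section is handled differently: its findings are presented "in the form of a shift table to detect changes from baseline". The section ends: "All hypersensitivity data will be listed by treatment group, visit and time point".

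Section 13.5 adds: "Descriptive statistics for actual values and changes from baseline of vital signs, weight and BSA will be presented by treatment group and visit". Section 5.5 fixes the reference: "The baseline value will be considered to be the last non-missing value before the first administration of study drug".

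**The concern.** The three readings exist so that a change around the infusion can be seen, yet the rule ignores the first when it judges the other two. A patient whose diastolic pressure is 92 before the infusion and 91 after it is counted as having a hypersensitivity result at both times, and again at every visit where the pattern repeats. The reading taken "within 15 minutes before the study drug infusion" cannot be a reaction to that infusion. No exclusion criterion names hypertension or bradycardia (criterion 8 covers severe cardiac disease), so such patients can be enrolled.

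The Protocol synopsis (Safety Assessments) and SAP section 13 both name vital signs as a means of assessing hypersensitivity, so this table is the planned summary of that assessment. At stake is whether a reader comparing the two products can tell a new post-infusion abnormality from one the patient already had.

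**Working it through.** The documents give no rate, power or error level for this table, so there is no figure to reproduce. The check is a reading of the sections against each other, with three small calculations.

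**1. How much of the table is pre-infusion.** Dosing visits: 4 induction + 12 maintenance = 16 (SAP section 4). Time points: 3. Parameters: 5.
- All doses: 16 × 3 × 5 = 240 cells per arm, of which 16 × 5 = 80 (one third) are pre-infusion.
- Through the first maintenance year: 10 × 3 × 5 = 150 cells, of which 50 are pre-infusion.

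**2. Whether another planned output shows same-day change.**
- Section 13.5 gives change from baseline by visit, not by time point. Baseline under section 5.5 is the last value before the first dose, not the pre-infusion value of the current cycle. Appendix 1 also places the routine vital signs of dosing visits before the infusion, and its note 27 describes the hypersensitivity readings as additional.
- The ECG shift in 13.7 is a within-patient comparison, although against the section 5.5 baseline. Vital signs get no shift of any kind.
- The listing shows each value but does not summarise. Through the first maintenance year it can hold up to 150 values per patient, or 174 × 150 = 26,100 at the initial sample size if everyone receives every dose.

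**3. What counts by time point can and cannot show.** Suppose (illustration only) 20 of 87 patients in an arm are notable before the infusion and 20 of 87 after.
- If the same 20 are abnormal both times, new onset is 0.
- If all 20 recovered and 20 others became abnormal, new onset is 20, or 20/87 = 23%.
- The table is identical in both cases.

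The text also splits by parameter without saying that low and high are shown separately. If they are pooled, a diastolic pressure going from 95 to 48 looks the same as one that stays at 95. No per-patient summary over all infusions is described.

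**4. Effect on the contrast between arms.** Let b be the share already outside a limit before the infusion and still outside it afterwards, and e the new-onset rate among the rest. The post-infusion flagged rate is b + (1 − b)e, so the difference between arms is (1 − b)(e₂ − e₁). The documents give neither b nor e. Assuming e = 5% in one arm and 15% in the other:

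| b | Flagged, e = 5% | Flagged, e = 15% | Difference | Ratio |
|---|---|---|---|---|
| 0% | 5.0% | 15.0% | 10.0 points | 3.0 |
| 10% | 14.5% | 23.5% | 9.0 points | 1.6 |
| 20% | 24.0% | 32.0% | 8.0 points | 1.3 |
| 30% | 33.5% | 40.5% | 7.0 points | 1.2 |

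Most of the absolute difference survives, while the relative contrast fades quickly. No test is planned for this table, so a power figure would have no use.

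**The case against.** The strongest reply is that the table already separates the time points. Pre-infusion counts are not pooled with post-infusion counts, and they give the background against which the later columns can be read in each arm. The listing allows any individual course to be followed. Infusion-related reactions do not depend on this table: section 13.1.5 identifies them from what is recorded on the adverse event page and lists them with symptoms, intensity and, where pressure fell, the lowest blood pressure after exposure. Counting values beyond fixed limits is a coherent descriptive summary, and the table shells are a separate addendum (SAP section 2) that is not available here.

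All of that stands, and it rules out a stronger reading. A reader might infer that the table hides real infusion effects, that background swamps the signal, or that this is the plan's objective measure of infusion reactions. The documents do not support these inferences. The time-point split and the listing keep the information accessible, reactions are captured elsewhere, and background rates should on average be alike in randomised arms and so favour neither product. Nor do the documents support any particular share of the counts being background.

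What the reply does not answer is the label on pre-infusion values and the absence of any summary of who changed. Marginal counts cannot supply that, and unseen shells are no substitute for a rule in the SAP.

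**Conclusion.** The point holds, with limited reach. As written, section 13.7 gives the hypersensitivity label to abnormal values that precede the infusion, in one third of the table's cells. It also leaves new post-infusion abnormality unsummarised, although the paired readings are collected for that purpose. The effect is confined to one descriptive safety table; the primary response-rate comparison and the reporting of infusion-related reactions are untouched. The label and the missing same-day comparison follow directly from the text. How far the contrast between arms is blunted depends on b and e, which are assumed, and on pre-infusion abnormalities persisting after the infusion.

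**What to change.** - Retitle the existing absolute-limit counts as clinically notable vital signs, and state that low and high are shown separately.
- For each parameter, add a shift table (low, normal, high by the SAP's own limits) from the same-day pre-infusion value to the end-of-infusion value and to the 60-minute value.
- From it, count patients who move into a low or high category they were not in before the infusion, including high to low and low to high. A rule that counted only patients with a normal pre-infusion value would miss, for example, a systolic pressure going from 165 to 85.
- Report this by visit and, per patient, for any infusion, with patients who have both readings as the denominator.

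A value that worsens within the same category, such as a heart rate going from 102 to 150, would still be visible only in the listing. The cost is SAP wording, one more table and its programming. All values are already collected.

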 26. Study drug (either CT-P10 or Rituxan), 375 mg/m² of BSA, will be administered on Day 1 of each cycle at 1 week intervals during Induction Study Period, and 8 weeks intervals during Maintenance Study Period. The first dose of study drug is to be administered at the same date with randomisation. Antipyretic (eg, paracetamol), antihistaminic (eg, H1 antihistamine), and glucocorticoid medications will be administered 30 minutes before each study drug infusion.
 27. 12-lead ECG will be obtained within 42 days before the first drug administration, EOT1, prior to Cycle 1 (Month 3; EOT2), Cycle 3 (Month 7), Cycle 6 (Month 13), Cycle 9 (Month 19) and the EOT3 visit during the Maintenance Study Period. Additional vital signs including systolic and diastolic blood pressure, heart rate, respiratory rate, and body temperature (before beginning the study drug infusion on Day 1 of each cycle [within 15 minutes before the beginning of the study drug infusion], at the end of study drug infusion [within 15 minutes after the end of the study drug infusion], and 60 minutes [±15 minutes] after the end of the study drug infusion) will be assessed to monitor for possible hypersensitivity reactions. In addition, hypersensitivity should be monitored by routine continuous clinical monitoring including ECG (3-lead or 12-lead) monitoring 60 minutes (±15 minutes) after the end of the study drug infusion. Emergency equipment, such as adrenaline, antihistamines, corticosteroids, and respiratory support (including inhalational therapy, oxygen, and artificial ventilator), must be available.
 28. Throughout the study, patients should be monitored for the clinical signs and symptoms of TB. Chest x-rays could also be used as a TB monitoring method. Patients with active TB will be excluded during the Screening Period. Chest x-rays for TB screening and clinical monitoring will be reviewed at the local level. Chest x-ray can be replaced by CT or proper image.
 29. All medications used during the study, as well as all medications taken from the signed date of the ICF until 30 days after the last dose of study drug administration or an EOT Visit, whichever is longer, will be recorded.

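### The SAP 13.7 shift table for the post-infusion ECG uses the single Screening ECG as its reference, so it cannot separate change around an infusion from change acquired earlier, although closer pre-infusion ECGs are already scheduled

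*SAP*

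**What the plan says.** - **Timing of the hypersensitivity ECG.** SAP 13.7 calls for "routine continuous clinical monitoring including ECG (3-lead or 12-lead) monitoring at 60 minutes" after the end of infusion, with a 15-minute tolerance. It names no ECG before the infusion.
- **Contrast with vital signs.** The same section takes hypersensitivity vital signs "within 15 minutes before the study drug infusion, within 15 minutes after the end of the study drug infusion and at 60 minutes" after it, on every dosing day.
- **Analysis.** The ECG findings (normal, abnormal not clinically significant, abnormal clinically significant) are shown "by treatment group and visit for the Safety population in the form of a shift table to detect changes from baseline". No baseline is defined in 13.7.
- **Baseline.** SAP 5.5: "The baseline value will be considered to be the last non-missing value before the first administration of study drug". This is one value per patient and is not reset at each infusion.
- **Scheduled 12-leads.** Appendix 1 (footnote 27) places them at Screening (within 42 days before the first dose), at EOT1, before Maintenance Cycles 1 and 3, and then at "Cycle 6 (Month 13), Cycle 9 (Month 19) and the EOT3 visit during the Maintenance Study Period". Footnote 8 marks the maintenance-cycle ECGs as done before that visit's infusion. None is scheduled before the infusion at Induction Cycle 1.
- **Where those ECGs are reported.** SAP 13.6 puts the scheduled 12-leads in their own by-visit shift table from baseline. Nothing links a 13.6 reading to the 13.7 reading from the same day.

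**The concern.** A table under a hypersensitivity heading should help the reader see whether the ECG changed around an infusion. With a study-level baseline it shows change since Screening. A patient who acquires a lasting abnormality between Screening and Maintenance Cycle 3 appears as a shift at Cycle 3 and at each later infusion while it lasts, even if that day's pre-infusion 12-lead already showed it.

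The recording type can also differ. The post-infusion reading may be 3-lead, while the reference is a 12-lead taken after supine rest (13.6). A 12-lead abnormality that a 3-lead does not show would appear as a shift towards normal.

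SAP 13 names hypersensitivity, via vital signs and ECG, among the safety endpoints, and this is the ECG part of that assessment. The point is clearest at Maintenance Cycle 7, when patients randomised to Rituxan can first receive CT-P10: the reference is still the ECG from before any study drug, although a pre-infusion 12-lead is scheduled one cycle earlier.

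**Working it through.** **Inputs.** SAP section 4 and Appendix 1: four weekly induction infusions (Weeks 1-4); first maintenance dose 8 weeks after the last induction dose; up to 12 maintenance cycles every 8 weeks; Screening window up to 42 days, which is 42/7 = 6 weeks. SAP 5.2: 87 patients per arm.

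**Step 1: reproduce the plan's calendar.** Maintenance Cycle k falls at Week 4 + 8k. Cycle 1 = Week 12, Cycle 6 = Week 52, Cycle 12 = Week 100, and EOT3 = 100 + 8 = Week 108. All agree with Appendix 1.

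**Step 2: age of each possible reference at the infusion.** Age of the Screening ECG runs from (W - 1) to (W - 1) + 6 weeks. Age of the latest scheduled pre-infusion 12-lead is W minus the week of that ECG.

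| Infusion | Week W | Screening ECG age (weeks) | Latest scheduled pre-infusion 12-lead | Its age (weeks) |
|---|---|---|---|---|
| Induction 1 | 1 | 0-6 | Screening | 0-6 |
| Induction 4 | 4 | 3-9 | Screening | 3-9 |
| Maintenance 1 | 12 | 11-17 | Maintenance 1 | 0 |
| Maintenance 2 | 20 | 19-25 | Maintenance 1 | 8 |
| Maintenance 3 | 28 | 27-33 | Maintenance 3 | 0 |
| Maintenance 5 | 44 | 43-49 | Maintenance 3 | 16 |
| Maintenance 6 | 52 | 51-57 | Maintenance 6 | 0 |
| Maintenance 7 | 60 | 59-65 | Maintenance 6 | 8 |
| Maintenance 9 | 76 | 75-81 | Maintenance 9 | 0 |
| Maintenance 12 | 100 | 99-105 | Maintenance 9 | 24 |

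If every dosing window were used in full (3 x 1 day + 12 x 7 days = 87 days, about 12 weeks), 105 would become about 117 weeks.

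**Step 3: same-visit comparators.** There are 4 + 12 = 16 possible infusions. A pre-infusion 12-lead is scheduled at 4 of them (Maintenance Cycles 1, 3, 6 and 9) and absent at 16 - 4 = 12 (75%).

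**Step 4: size at one visit.** The documents give no background ECG rate. Assume that by a given visit a proportion p of patients has a lasting ECG category change since Screening that has nothing to do with infusion, and that all 87 per arm are still treated:

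- p = 2%: 87 x 0.02 = 1.7, about 2 patients
- p = 5%: 87 x 0.05 = 4.4, about 4 patients
- p = 10%: 87 x 0.10 = 8.7, about 9 patients

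If 2%, 5% or 10% is read instead as a rate per year, the proportion shifted after t weeks is 1 - (1 - r)^(t/52): 0.2%, 0.6% or 1.2% at 6 weeks, 2.2%, 5.5% or 10.9% at 57 weeks, and 4.0%, 9.8% or 19.2% at 105 weeks. The unwanted component grows with the age of the reference.

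**The case against.** The strongest defence is that one study-level baseline is the SAP's convention throughout (vital signs, ECG, physical examination), that the table is descriptive with no test, and that detecting infusion effects does not depend on it. Vital signs are taken before and after every infusion. Infusion-related reactions are an adverse event of special interest, with timing, symptoms and lowest blood pressure recorded (13.1.5). The protocol synopsis describes hypersensitivity assessment through vital signs only. The 13.6 table and the listings let a reader compare pre- and post-infusion ECGs at four visits. The table shells, which could define the reference, are a separate addendum. All of this stands and limits the weight of the point. It does not supply the comparison: two marginal tables, each against Screening, do not show within-patient change around an infusion.

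A moving reference also has a fair objection: a lasting abnormality that arises after one infusion becomes part of the next reference and drops out of the table. Keeping the Screening shift in 13.6 largely answers this.

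A reader might infer more than the documents support:

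- *That no pre-infusion ECG exists.* That is true of the 13.7 procedure and of 12 of 16 infusions, but four visits have one.
- *That the SAP counts every later change as an infusion effect.* It speaks only of change from baseline and sets no attribution rule.
- *That 105 weeks is typical.* It arises only in the optional second year, when all treated patients receive CT-P10. The maximum is 57 weeks through Cycle 6, and 25 weeks for the first CSR, whose data stop before Maintenance Cycle 3, so that Cycle 2 is its last infusion.
- *That dozens of false cases would appear.* Multiplying the assumed 5% across 6 cycles gives 87 x 0.05 x 6 = 26, but this recounts the same patients. The planned table counts patients per visit.
- *That the arms are biased against each other.* Background change should be similar in both randomised arms.

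**Conclusion.** The point holds as a low-severity improvement. Under SAP 5.5 and Appendix 1, the 13.7 ECG table compares each post-infusion reading with one Screening 12-lead, nominally up to 17, 57 and 105 weeks old at Maintenance Cycles 1, 6 and 12. It cannot separate change around the infusion from earlier change, and it may mix recording types. The likely effect is dilution: about 4 of 87 patients per arm at a visit on an assumed 5% background rate (2-9 patients over 2-10%), fewer if patients have stopped treatment. The primary analysis is not affected.

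This rests on three assumptions: that the Screening ECG is the baseline, which 13.7 does not state but which follows from 5.5 and the schedule unless an unscheduled pre-dose ECG exists; that visits follow the nominal calendar; and the background rate, which comes from outside the documents.

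**What to change.** In SAP 13.7, define the reference for the post-infusion ECG:

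1. At Maintenance Cycles 1, 3, 6 and 9, give a paired pre/post-infusion shift against the same-visit pre-infusion 12-lead.
2. At other infusions, use the most recent scheduled pre-infusion 12-lead and footnote its age: Screening for Induction Cycles 1-4; Maintenance Cycle 1 for Cycle 2; Cycle 3 for Cycles 4-5; Cycle 6 for Cycles 7-8; Cycle 9 for Cycles 10-12. The nominal age in maintenance is then at most 24 weeks, against 105.
3. Keep the shift from Screening in 13.6, so that lasting changes stay visible.
4. Show 3-lead and 12-lead post-infusion results separately if lead type is recorded; if it is not, say so in a footnote.

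The cost is SAP wording, modest programming and a table footnote, with no new ECGs. The reference will differ by cycle, which the footnote must explain. The remaining limit is that 12 of 16 infusions still have no same-visit comparator, and the table should state this.

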13.8. Tuberculosis Assessment

During the Screening Period, a current diagnosis of active TB or examination findings indicating the presence of active TB will result in patient exclusion from the study. TB assessment will be performed at the time points specified in the [APPENDIX 1](#). Findings will be classified as {‘Normal’, ‘Abnormal, not clinically significant’ and ‘Abnormal, clinically significant’}.

The number and percentage of patients who have TB assessment results will be summarized by treatment group and visit for the Safety population. All TB data will be listed by treatment group and visit.

13.9. Physical Examination

Physical examinations with particular attention to infections and PML will be performed at the time points specified in the [APPENDIX 1](#). Information of physical examination will be recorded in the ‘Physical Examination’ or the ‘Adverse Event’ page of the eCRF in case any new abnormality in post-screening is detected.

Findings will be classified as {‘Normal’, ‘Abnormal, not clinically significant’ and ‘Abnormal, clinically significant’}. The number and percentage of patients will be provided, by treatment group and visit for the Safety population, in the form of a shift table to detect changes from baseline. All physical examination data will be listed by treatment group and visit.

